9.2 Sample Size and Accrual Rate

Approximately 135 eligible subjects will be enrolled in this multicenter clinical trial that will be conducted at approximately 25 UPMC sites and up to 5 external sites in North America.

The first primary objective is to demonstrate that TORS with de-escalation RT (50Gy) and Nivolumab is equivalent (not inferior) to the standard of care of chemotherapy + standard 60-66 Gy radiation. The first primary endpoint is probability of progression free survival where an event is any type of disease progression or recurrence (local, regional or distant). In this definition deaths from other cancers, other non-cancer causes or treatment related deaths are censored. The historical control for the study is based part upon the results of Huang ⁹ in which the probability of 3 year OS was approximately 65% for high risk (Group III, T4 or N3, age < 70) HPV+ patients treated with chemoradiation and that 3 year OS is an approximation of two year PFS. Since there is not an ideal, published cohort to use, the trial is designed to investigate whether TORS with 50 Gy RT + Nivolumab is not inferior to standard of care chemotherapy + standard 60-66 Gy radiation.

We plan to devote 2 years of accrual and one year of additional follow-up. We assume that the experimental arm is not inferior to the standard if the 2-year PFS is not less than 55%, 10% less than the assumed standard. Thus 55% 2-year TTP for de-escalation RT + Nivolumab is considered not inferior to the 65% 2-year PFS for Cisplatin + 60-66 Gy RT.

Using a one-tailed exponential test (using the maximum likelihood estimator for the hazard rate of the exponential distribution) at $\alpha = .10$, 135 patients will provide 90% power to reject the null hypothesis that the experimental arm is inferior (less than 55% 2-year PFS) when the underlying 2-year PFS is 65%.

The second primary objective is to demonstrate reduction in feeding tube dependence. We will compare 1-year PEG tube dependence for patients who have not progressed to the SOC. Based on

unpublished results from RTOG 0234 for 84 patients treated with RT + cisplatin + cetuximab, 67 (80%) did not have disease progression at one year. Of these, 11 (16%) were dependent upon a feeding tube one year after the start of treatment. Assuming a 15% PEG tube SOC rate, we wish to demonstrate a 50% improvement or to 7.5% due to the proposed de-escalation regimen. We assume the same 1 year non-progression rate of 80% which suggests 80% of 135 or 108 patients will be candidates for a feeding tube at one year. A one tailed exact binomial test with 108 patients at alpha = .06 will have 80% power to detect a reduction in 1 year PEG tube rate from 15% to 7.5%. Using the Bonferroni inequality, the type I error for testing both primary hypotheses is 16% with 135 patients.

Thus, we require accrual of 45 patients/yr for 3 years (135 total) with one year of additional follow-up.

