Phase II Trial of Adjuvant De-Escalated Radiation + Concurrent and Adjuvant Nivolumab for Intermediate-High Risk P16+ Oropharynx Cancer

STUDY CHAIR: [name]. Ph.D.
STUDY CO-CHAIR: [name].
MEDICAL ONCOLOGY CO-CHAIR: [name].
RADIATION THERAPY CO-CHAIR: [name], M.D., Ph.D.
SURGICAL CO-CHAIR: [name].
STUDY STATISTICIAN: [name], M.S.
CORRELATIVES CO-CHAIR: [name]., Ph.D.

Version Date: December 03, 2020

Agents	IND#	Supply
nivolumab	141,230	Investigational

[figure not shown]
Study Co-Chair

[name]., Ph.D.
[name]
Hillman Cancer Center, [name]
[name]
[contact]
[contact]
Email: [contact]

Study Co-Chair

[name].
Helen F. Graham Cancer Center
[name]
[name]
[name]
[contact]
Email: [contact]

Phase II Trial of Adjuvant De-Escalated Radiation + Concurrent Nivolumab for Intermediate-Risk P16+ Oropharynx Cancer

Co-Primary endpoints: 2-year Disease-free survival, 1-year PEG dependence

Secondary endpoints: QOL, Distant metastatic control, locoregional control, overall survival

Paired tumor/TME/blood biomarkers

Nivolumab will be administered at 240 mg IV q2 weeks during radiotherapy, and at 480 mg IV q4 weeks for 6 doses after RT. Radiotherapy to receive IMRT to 50 Gy/2 Gy per fraction/6 fxs per week, with the first dose of nivolumab delivered at day -3 ± 2 days prior to RT. RT will be delivered daily for 4 days, with 2 fractions on day 5 per week. After 4 weeks, this will total 48Gy, with an additional day to reach 50Gy.

Eligibility Overview:

Inclusion (AJCC 7th Edition):

- P16+ squamous cell carcinoma of the oropharynx
- Tobacco <10 pack years (pk-yr): T0-3 plus any one of the following: >N2b (> 5 LN's +), N2c/N3, +ENE >1 mm, or + margin (if approved by surgical chair) OR
- Tobacco >10 pk-yr: T0-3 plus any one of the following: any N2, N3, +ENE >1 mm, or + margin (if approved by surgical chair)
- M0
- Age >18, gender neutral
- ECOG performance Status 0-1
- Patients must have undergone gross surgical removal with transoral surgery + neck dissection for p16+ OPC
- Patients undergoing tonsillectomy are eligible and do not require additional surgery if all gross disease removed
- Adequate hematologic, renal and hepatic function for cisplatin

Exclusion:

- P16-negative
- T4 primary
- T4, or ≤N1
- Gross residual disease after surgery
- Female patient lactating or pregnant
- Prior radiation or chemotherapy for head and neck cancer
- Prior immunotherapy agents

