6.1 Time to Progression

This interval will be measured from the date of entry on the study to the appearance of new metastatic lesions or objective tumor progression.

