9.1 Objectives

The dual primary objectives of this phase II study are (1) test the hypothesis that the proposed adjuvant de-escalation strategy (TORS + 50Gy RT + Nivolumab cancer) has equivalent (non-inferior) 2-year PFS. PFS is survival without local, regional or distant disease progression; patients who do not progress or die while disease – free will be censored and (2) to demonstrate a reduction in the rate of PEG tube dependence at one year.

Secondary objectives include estimating recurrence patterns, assessing quality of life (QOL) and swallowing function before and after treatment and evaluating toxicity.

With improved outcomes for p16+ oropharyngeal cancers treatment de-escalation is a critical and topical subject for a controlled clinical. This trial tests the hypothesis that de-escalating treatment of intermediate risk p16+ oropharyngeal cancer patients benefits them by providing equivalent oncologic outcome with superior quality of life.

The first hypothesis to be tested is that oncologic outcome following de-escalation is clinically equivalent to conventional standard systemic therapy with transoral robotic surgery (TORS) plus adjuvant cisplatin and 60-66 Gy radiation. The definition of non-inferiority is clearly within a desired clinical window of equivalence, defined as 2-year PFS, not less than 10% lower than expected under standard-of-care. Therefore, the design is to establish the non-inferiority of the experimental therapy (TORS + Nivolumab + 50 Gy radiation). The second hypothesis to be tested is de-escalation is warranted, by virtue of a clinically meaningful improvement in quality of life as measured by reduced G tube patency.

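### The first co-primary endpoint is called PFS (DFS in the schema) but counts only progression and censors treatment-related and other deaths, while its 55% threshold is stated as PFS

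*Combined protocol and SAP*

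**What the plan says.** The first co-primary endpoint appears under three names.

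- **Study schema:** "Co-Primary endpoints: 2-year Disease-free survival, 1-year PEG dependence".
- **Section 9.1:** PFS, described as survival free of local, regional or distant progression, with the rider that "patients who do not progress or die while disease – free will be censored".
- **Section 9.2:** PFS, with any progression or recurrence as the event. It adds: "In this definition deaths from other cancers, other non-cancer causes or treatment related deaths are censored".

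Section 9.2 writes the non-inferiority rule and the null hypothesis as 2-year PFS of 55%, ten points below an assumed 65%. Between the two it says: "Thus 55% 2-year TTP for de-escalation RT + Nivolumab is considered not inferior to the 65% 2-year PFS". The 65% comes from a published 3-year survival figure, on the ground that "3 year OS is an approximation of two year PFS".

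Section 6.1 defines time to progression as running from study entry to "the appearance of new metastatic lesions or objective tumor progression". Death is not an event there.

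The test is a one-sided exponential test at 0.10 with 135 patients and 90% power. Section 9.2 gives two accrual plans: "We plan to devote 2 years of accrual and one year of additional follow-up", and later "we require accrual of 45 patients/yr for 3 years (135 total) with one year of additional follow-up".

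**The concern.** Name, event rule and threshold do not describe one quantity. The event rule in 9.2 is that of TTP. The rule and null are on the PFS scale. One sentence sets a TTP for the new regimen against a PFS for the control. The benchmark behind both numbers is overall survival, which counts every death.

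Section 9.1 does not settle the matter. Its rider can mean that patients who die disease-free are censored, or that only patients who neither progress nor die are censored. Where the background sections (1.2 and 1.5) report PFS-type results from other studies, the event is progression or death, so a reader will expect that meaning.

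The trial replaces cisplatin with nivolumab and lowers the radiation dose, and it aims to claim an oncologic outcome that is not inferior. Under the rule as written, a death caused by the regimen is removed from the primary oncologic test. With the threshold held at 55%, this can only make non-inferiority easier to declare.

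**Working it through.** **1. The plan's own figure.** Inputs from 9.2: N = 135, 2-year rates of 55% (null) and 65% (alternative), one-sided 0.10. Exponential hazards per year:

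- null: λ0 = −ln(0.55)/2 = 0.2989
- alternative: λ1 = −ln(0.65)/2 = 0.2154
- ratio 1.388, ln = 0.3277

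With uniform entry over A years, F further years of follow-up and no dropout, the expected number of events is d = N·[1 − (e^(−λF) − e^(−λ(A+F)))/(λA)]. Power is Φ{[ln(λ0/λ1) − 1.2816/√d0]·√d1}.

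- 3+1 years: d0 = 68.9, d1 = 54.8. (0.3277 − 0.1544) × 7.403 = 1.283, so power is **90.0%**. This reproduces the plan.
- 2+1 years: d0 = 59.6, d1 = 46.6. (0.3277 − 0.1660) × 6.826 = 1.104, so power is **86.5%**.

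The arithmetic is the same whether the percentages are called PFS or TTP, so it does not show which was meant. Both accrual plans are carried forward.

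**2. Direction.** Observation for this endpoint stops at death whether the death is an event or a censoring, so person-years are the same. On the log scale the upper bound for the hazard depends on the event count d through ln(d) + 1.2816/√d. Its derivative, (1/d)(1 − 0.6408/√d), is positive for every d ≥ 1. Counting a death therefore never makes non-inferiority easier.

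**3. Size.** The documents give no rate of death without progression here, so the net 2-year risk q is an assumption. True all-cause PFS is fixed at 55%. The total hazard of 0.2989 is split into death, −ln(1 − q)/2, and progression (the rest). The corresponding 2-year TTP is 0.55/(1 − q). The log-scale test was simulated with 200,000 trials per cell:

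| q | 2-year TTP when PFS is 55% | False non-inferiority, deaths censored, 3+1 | Same, 2+1 |
|---|---|---|---|
| 0% | 55.0% | 9.4% | 9.5% |
| 1% | 55.6% | 12.1% | 11.6% |
| 2% | 56.1% | 15.1% | 14.6% |
| 3% | 56.7% | 18.7% | 18.0% |
| 5% | 57.9% | 27.6% | 26.0% |

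With deaths counted, the rate is 9.2-9.5% throughout. With the cut-off calibrated to exactly 10% instead, the deaths-censored rates at q = 2% and 5% are 16.1% and 29.5% (3+1) or 15.7% and 27.6% (2+1).

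**4. The only anchor in the documents.** Section 1.5 reports 3 drug-related deaths among 306 patients in one nivolumab study and 1 among 268 in another. That gives 3/306 = 1.0%, or pooled 4/574 = 0.7%: 1.3 or 0.9 expected deaths in 135 patients. Used as a crude 2-year risk (80,000 trials per cell), with the lower rate first:

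- constant hazard: 11.7% and 12.9% (3+1); 11.5% and 12.7% (2+1)
- all such deaths in the first 7 months: 11.3% and 12.2% (3+1); 11.1% and 11.8% (2+1)

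**5. One death at the boundary, with no assumed death rate.** The statistic is ln[(d/T)/λ0]·√d and passes below −1.282.

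- T = 254.2 person-years (expected for 3+1 and a true 65%): d = 64 gives ln(0.8423) × 8 = −1.373 and passes; d = 65 gives −1.259 and fails.
- T = 216.5 person-years (2+1): d = 54 gives −1.330 and passes; d = 55 gives −1.206 and fails.

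So under 3+1 years, 64 progressions and one treatment-related death pass as the plan is written and fail if the death counts.

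**The case against.** The strongest reply is that the rule in 9.2 is explicit and can be applied without guessing. Section 6.1 has the same progression-only event, and 9.2 arguably resolves the rider in 9.1. If the 55% is a TTP figure, as one sentence says, the test keeps its error rate. The inflated rates then measure the distance between two estimands and do not show a faulty test. That is correct as far as it goes. But the null and the decision rule are written as PFS, and that null is not the quantity the event rule tests.

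Second, the effect at the anchor is small and the anchor is weak. It uses crude proportions from metastatic patients without radiotherapy, covers drug-related deaths only, and includes one case complicated by lymphangitic spread. The test scale, which 9.2 leaves open, matters almost as much: with no such deaths, an untransformed Wald test has an error of about 11.2%, against 9.5% on the log scale. The boundary also moves by one event on that scale, to 65 pass and 66 fail (55 and 56 for 2+1). These points stand. The boundary is an illustration, and the 2-5% rows are assumptions.

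Third, deaths are not hidden. Section 9.3 plans overall survival and the cumulative incidence of death without progression, and 9.4 monitors dose-limiting toxicity. This limits the practical harm, but none of it enters the primary test.

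Fourth, 3-year survival matches neither PFS nor TTP, and 9.1 also names a cisplatin arm of an earlier trial as the comparison. No net bias against standard of care can be inferred from the benchmark, and none is claimed.

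**Conclusion.** The concern holds. The plan names PFS or DFS, analyses TTP, and states its null on the PFS scale. The direction at a fixed 55% threshold is certain; the size is not. Under constant hazards, 135 patients and a true all-cause PFS of 55%, the one-sided error is about 11-13% at the documents' own drug-related death rates, including when all those deaths fall early. It rises to about 26-28% only at an assumed 5% risk of death without progression, and the effect vanishes as that risk nears zero. The error rate is as stated for TTP. This should be fixed before analysis, but it does not by itself invalidate the design.

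**What to change.** In 9.1 and 9.2, define the primary event as local, regional or distant progression or recurrence, or death from any cause. Reword the rider in 9.1 to match, use one endpoint name everywhere including the schema, and state that 65% and 55% are all-cause PFS. Keep the deaths-censored version as a secondary TTP, aligned with 6.1 and reported beside the cumulative incidence in 9.3.

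If the sponsor does intend TTP as primary, it should rename the endpoint, drop the PFS and DFS claims, and justify 65% and 55% on the TTP scale.

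Data collection does not change, because survival is already followed for 5 years (5.7) and deaths are analysed in 9.3. The observed rate may look slightly less favourable. If 65% is all-cause PFS, power with deaths counted is about 90% with 3+1 years and about 86% with 2+1. The latter is also the figure with no such deaths, so the accrual conflict needs its own correction. If 65% was meant as TTP, true PFS is 0.65 × (1 − q), and power must be restated:

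| Net risk q | PFS | Power, 3+1 | Power, 2+1 |
|---|---|---|---|
| 1% | 64.35% | 86% | 82% |
| 2% | 63.70% | 82% | 77% |
| 3% | 63.05% | 77% | 72% |
| 5% | 61.75% | 66% | 61% |

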The decision to select a single arm trial is based on the following: A two arm randomized non-inferiority trial would be prohibitively expensive, infeasible (approximately 600 patients would be needed) and delay results for five years. This single-arm trial is feasible and is powered to produce a definitive result in 3 years from 1st accrual. The comparison is a to large-well characterized contemporaneous subset of the ECOG 3311 trial with similar pathologic features as we propose in our new trial, that received cisplatin and standard dose radiotherapy in Arm D of ECOG 3311. Patients recruited to ECOG 3311 are expected to be similar to our patients at the University of Pittsburgh, a large tertiary-care academic medical center, in part since we were the #1 largest accrue in the US to ECOG 3311 ([name] is PI of that trial as well).

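### The primary PFS test shows only that 2-year PFS exceeds a fixed 55%; the unconditional non-inferiority claim, and the stated ECOG 3311 Arm D comparison, need a standard that the plan assumes and an analysis that it does not contain

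*Combined protocol and SAP*

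**What the plan says.** Three adjoining parts of Section 9 describe the primary PFS comparison differently.

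- **Section 9.1, definition.** Non-inferiority is relative to standard of care: 2-year PFS "not less than 10% lower than expected under standard-of-care".
- **Section 9.1, rationale for a single arm.** The comparison is said to be with a subset of patients "that received cisplatin and standard dose radiotherapy in Arm D of ECOG 3311". The trial is described as "powered to produce a definitive result in 3 years from 1st accrual".
- **Section 9.2, sample size.** The regimen is judged "not inferior to the standard if the 2-year PFS is not less than 55%, 10% less than the assumed standard". The test is a one-sided, one-sample exponential test at alpha 0.10 with 135 patients. The stated power is 90% when true 2-year PFS is 65%.

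The 65% rests in part on a report in which "3 year OS was approximately 65% for high risk (Group III, T4 or N3, age < 70) HPV+ patients treated with chemoradiation", with 3-year OS taken to approximate 2-year PFS. No other part of the basis is described. Section 9.2 qualifies this openly: "Since there is not an ideal, published cohort to use". For the PFS endpoint, "deaths from other cancers, other non-cancer causes or treatment related deaths are censored".

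The opening of Section 9 and the objective in Section 2.1 claim equivalence or non-inferiority to standard of care without tying it to an assumed rate.

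**The concern.** A one-sample test against 55% answers whether 2-year PFS exceeds 55%. It also answers whether the regimen is within 10 points of standard at the nominal error rate only if the standard is 65%. Arm D could have supplied the missing link, but Section 9 gives no Arm D PFS rate, number of patients, rule for choosing the subset, or primary analysis that uses those patients.

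The named source for 65% also differs from this trial. It includes T4 disease, which is excluded here. Its patients had chemoradiation, whereas all patients here are resected. It counts all deaths, whereas this endpoint censors deaths without progression. It is also limited to age under 70, while Section 3.1 sets no upper age limit. These differences need not all point the same way.

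At stake is a conclusion of non-inferiority to cisplatin plus 60-66 Gy, in a curative setting, for a regimen that could be more than 10 points worse.

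**Working it through.** **Inputs (Section 9.2).** n = 135; one-sided alpha 0.10 (z = 1.2816); null 55%; alternative 65%. Two accrual plans appear: "We plan to devote 2 years of accrual and one year of additional follow-up" (2+1), and, at the end of the section, 45 patients a year for 3 years plus one year (3+1). Both are carried through. I assume uniform accrual and no dropout, as none is stated.

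**Formulas.** With A years of accrual and F of follow-up:

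- Hazard: h = -ln(S)/2.
- Event probability: p = 1 - (e^(-hF) - e^(-h(A+F)))/(hA).
- Hazard scale: critical hazard hc = h0(1 - z/√(n·p0)); P(pass) = Φ[(hc - h)/(h/√(n·p))].
- Log-hazard scale: hc = h0·e^(-z/√(n·p0)); P(pass) = Φ[ln(hc/h)·√(n·p)].

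**Reproducing the plan's figure (3+1, hazard scale).**

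- h0 = -ln(0.55)/2 = 0.2989 and p0 = 0.510, giving 68.9 expected null events.
- hc = 0.2989 × (1 - 1.2816/√68.9) = 0.2528, an observed 2-year PFS of e^(-2×0.2528) = 60.3%.
- At 65%, h = 0.2154 with 54.8 events. Power = Φ[(0.2528 - 0.2154)/(0.2154/√54.8)] = Φ(1.285) = 90%.

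The stated power therefore reproduces under 3+1. Under 2+1 it is 86-87%. Across scales and plans, an observed 2-year PFS of about 60% (59.9-60.7%) is enough to pass.

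**Changing only the true standard (3+1, hazard scale).**

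- Standard 67.5%, regimen 57.5%: h = 0.2767, 65.4 events. Φ[(0.2528 - 0.2767)/(0.2767/√65.4)] = Φ(-0.70) = 24%.
- Standard 70%, regimen 60%: h = 0.2554, 62.0 events. Φ[(0.2528 - 0.2554)/(0.2554/√62.0)] = Φ(-0.08) = 47%.

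**Full range** (both scales, both accrual plans):

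| True standard | Margin implied by 55% floor | Regimen exactly 10 points worse passes | Regimen equal to standard passes |
|---|---|---|---|
| 60% | 5 points | 0.4-1.1% | 43-51% |
| 62.5% | 7.5 points | 2.6-3.6% | 67-74% |
| 65% | 10 points | 10% (nominal) | 86-90% |
| 67.5% | 12.5 points | 23-27% | 95-98% |
| 70% | 15 points | 43-51% | about 99% |
| 75% (assumed) | 20 points | 86-90% | above 99% |

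Simulation gives the same ranges: 23-27% at a true 57.5% and 43-51% at a true 60%. An assumed 5% yearly dropout leaves the log-hazard results inside them (25-26% and 46-50%).

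**The case against.** The strongest reply is that the assumption is disclosed and the benchmark is reasonable. Section 9.2 calls the standard assumed and concedes that no ideal cohort exists. The hypothesis text in Section 2.1 refers to historical results. A fixed benchmark is inherent in a single-arm phase II trial, which Section 9.1 justifies on cost and feasibility and Section 1.3 presents as preparation for a randomised phase III trial. Section 1.2 gives 60-70% 2-year PFS for patients with more than 10 pack-years and N2-N3 disease, and 65% is the midpoint.

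All of that stands, and it limits the point to what the conclusion may claim. It does not supply an Arm D analysis, and it does not make the unconditional statements in Sections 2.1, 9 and 9.1 follow from the test.

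A reader might infer more than the documents support:

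- **That 65% is too low.** Not shown. The 85% 2-year PFS and the prognosis near 90% cited in Section 1.2 describe broader HPV-positive groups, not resected patients selected for adverse features. Standards above 70% are assumptions.
- **That the non-inferiority claim fails in both directions.** It does not. If the standard is below 65%, passing still implies a deficit of less than 10 points. Only power suffers.
- **That no Arm D rate appears because ECOG 3311 had not reported.** The background describes that trial as ongoing, but the documents do not say why the rate is absent.

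**Conclusion.** The point holds as an inconsistency about the comparator and an over-broad conclusion, not as an error in the sample size or proof of a wrong benchmark. Sections 9.1 and 9.2 should agree on what is tested. As written, the test supports the claim that 2-year PFS exceeds 55%. It supports non-inferiority within 10 points, at the nominal error rate or better, only if the true standard is 65% or lower.

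Within the protocol's own 60-70% range, the chance of passing a regimen exactly 10 points worse runs from about 1% to 43-51%. A regimen equal to a 60% standard has only about an even chance of passing. These figures assume exponential event times, uniform accrual and no dropout. Which of them applies depends on a standard that the plan does not estimate. The inconsistency is certain; the size of the false-pass risk is conditional. It should be fixed, because it changes what can be concluded and the repair is small.

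**What to change.** Keep the 55% floor, the 135 patients and alpha 0.10. Then:

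1. In Sections 2.1, 9, 9.1 and 9.2, state the primary conclusion as 2-year PFS exceeding 55%, with non-inferiority to standard of care conditional on an assumed 65% standard.
2. Remove the description of the result as definitive in Section 9.1.
3. Reconcile Section 9.1 with Section 9.2. Either label the Arm D comparison supportive, with a subset rule, and report it as a difference with a confidence interval, or remove the statement that Arm D is the comparator.
4. Add a short table of implied margin and false-pass risk by true standard, using 60-70% from Section 1.2 and marking higher values as assumed.

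The cost is rewording four sections and adding one table. The design is unchanged, and the downside is a narrower primary claim, which still serves the purpose of guiding a phase III trial. If the Arm D difference is kept, its precision will depend on the size of that subset, which the documents do not give.

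### Sections 9.1 and 9.2 give two incompatible schedules for the same 135 patients; the stated 90% power for PFS fits 3+1 years, while 2+1 years gives about 86%

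*Combined protocol and SAP*

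**What the plan says.** Three statements in the current text describe the schedule for the same sample of 135:

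- Section 9.1, in the argument for a single-arm design, says the trial "is powered to produce a definitive result in 3 years from 1st accrual".
- Section 9.2, just before the PFS power statement: "We plan to devote 2 years of accrual and one year of additional follow-up".
- Section 9.2, closing sentence: "Thus, we require accrual of 45 patients/yr for 3 years (135 total) with one year of additional follow-up".

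Between the last two, Section 9.2 states the PFS power. The test is a one-tailed exponential test "using the maximum likelihood estimator for the hazard rate of the exponential distribution", at alpha 0.10, and "135 patients will provide 90% power to reject the null hypothesis that the experimental arm is inferior" (2-year PFS below 55%) when true 2-year PFS is 65%. The power sentence does not say which schedule it used.

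**The concern.** Sections 9.1 and 9.2 (opening) describe two years of accrual plus one year, so data are read three years after the first patient enters. Section 9.2 (close) describes three years plus one, so data are read at four years. The accrual rates differ too: 135 / 2 = 67.5 a year against 135 / 3 = 45 a year.

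This affects more than timing. The precision of an estimated exponential hazard depends on the number of events, and a shorter trial has fewer. One power figure cannot serve both schedules.

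Two things are at stake:

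- The plan has no single time for the primary PFS analysis. If it is read at the earlier time, the real power may be below the stated 90%.
- Section 9.1 justifies the single-arm design partly by speed, setting a three-year result against a randomized trial that would take five. Under the closing sentence of Section 9.2 the result comes at about four.

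**Working it through.** **Inputs from Section 9.2.** N = 135; one-sided alpha 0.10 (z = 1.2816); null 2-year PFS 55%; alternative 65%; exponential survival.

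**Assumptions, because the plan is silent.** Accrual is uniform, and there is no loss to follow-up or other censoring.

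**Hazards.**
- Null: λ0 = −ln(0.55)/2 = 0.2989 per year
- Alternative: λ1 = −ln(0.65)/2 = 0.2154 per year
- Difference: 0.0835

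**Probability of an observed event**, with accrual A and further follow-up F:

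p(λ) = 1 − [exp(−λF) − exp(−λ(A+F))] / (λA)

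**Power**, with the null standard error for the cut-off and the alternative one for power:

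Power = Φ{ [λ0 − λ1 − 1.2816·SE0] / SE1 }, where SEi = λi / √(N·pi)

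**Reproducing the plan's figure, 3+1.**
- p0 = 0.510 and p1 = 0.406, so 68.9 expected events under the null and 54.8 under the alternative (about 255 patient-years)
- SE0 = 0.2989/√68.9 = 0.0360; SE1 = 0.2154/√54.8 = 0.0291
- (0.0835 − 1.2816 × 0.0360)/0.0291 = 1.285, so power = 90.1%
- The smallest N giving 90% is 135

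**Same calculation, 2+1.**
- p0 = 0.442 and p1 = 0.345, so 59.6 and 46.6 expected events (about 216 patient-years)
- SE0 = 0.2989/√59.6 = 0.0387; SE1 = 0.2154/√46.6 = 0.0316
- (0.0835 − 1.2816 × 0.0387)/0.0316 = 1.075, so power = 85.9%
- The smallest N giving 90% is 157

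**Sensitivity to the unstated formula.**

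| Version | Power 3+1 | Power 2+1 | N for 90%, 3+1 | N for 90%, 2+1 |
|---|---|---|---|---|
| Hazard, both variances | 90.1% | 85.9% | 135 | 157 |
| Log hazard, both variances | 90.0% | 86.5% | 135 | 158 |
| Cube-root hazard, both variances | 90.1% | 86.4% | 135 | 157 |
| 2-year PFS from the MLE, both variances | 90.4% | 86.6% | 133 | 155 |
| One-sample log-rank | 91.3% | 87.2% | 128 | 151 |
| Hazard, alternative variance only | 94.4% | 91.4% | 108 | 127 |
| Hazard, null variance only | 85.0% | 81.0% | 165 | 191 |
| Log hazard, alternative variance only | 87.4% | 83.0% | 151 | 178 |
| Log hazard, null variance only | 92.5% | 89.4% | 120 | 139 |

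Three versions return exactly 135 under 3+1. None does so under 2+1.

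**Simulation.** The hazard MLE test was simulated with its cut-off set to give exactly 10% type I error, so no variance formula is needed. With 400,000 runs, power was 90.3% under 3+1 and 86.6% under 2+1.

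**Mixed readings.** Two further cases follow if statements from the two schedules are combined:
- 45 a year for only two years gives 90 patients and, under 2+1, 72% (hazard) to 76% (log hazard) power.
- 45 a year for three years, read at three years, leaves no further follow-up: about 36 expected events and 77% to 80% power.

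**The case against.** The best reply is that the closing sentence of Section 9.2 is the operative requirement. Its arithmetic closes (45 × 3 = 135) and it reproduces the 90%. On that reading the other two statements are leftover wording and the trial is not underpowered for this reason. That is plausible, and it makes the power loss conditional. It does not remove the conflict: two statements still give a three-year result, and nothing elsewhere settles it. Section 5.7 sets follow-up for each patient, not an analysis time.

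The second reply is that the plan names neither scale nor variance convention, and gives its sample size as approximate. Two single-variance shortcuts put 2+1 at 89.4% and 91.4%, close to 90%. This stands as a caveat, since the sponsor's actual calculation is not shown. But those shortcuts imply 139 and 127 patients under 2+1, not 135, and the simulation, which uses no variance formula, gives 86.6%.

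The third reply is that the shortfall is small. It is: 3.7 points by simulation and 4.2 by the hazard-scale formula. It also concerns only the PFS co-primary endpoint. The PEG-tube calculation uses 108 patients at one year and does not depend on accrual length.

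**Conclusion.** The concern holds. Sections 9.1 and 9.2 give two primary analysis times a year apart and two accrual rates for one sample; this needs no assumption.

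The stated 90% belongs to 3+1. Under 2+1, with all 135 patients enrolled within two years, power is about 86% to 87%, and type II error is about 13% to 14% instead of 10%. This rests on uniform accrual, no other censoring, and a formula using both variances, which is the type that returns 135.

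Other censoring would lower both figures. Section 9.2 censors deaths without progression and gives no rate for them. If such censoring ran at 2% to 5% a year (an assumption), 3+1 power on the hazard scale would be about 89.5% to 88.5%, and 2+1 power about 85.3% to 84.4%.

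This should be corrected, but it is not a fatal flaw.

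**What to change.** State one accrual period, one accrual rate, one follow-up period and one primary PFS analysis time in Sections 9.1 and 9.2. Name the power formula and its censoring assumption, and tie the power to that schedule. Coherent choices, under the assumptions above, are:

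- **3+1 at 45 a year.** Keep 135 patients and 90%, and change the time to result in Section 9.1 to about four years. This is a wording change; the cost is one year on the stated timeline.
- **2+1 at 67.5 a year.** Keep 135 patients and the three-year result, and restate power as about 86%. The cost is 50% faster accrual than now stated (67.5/45 = 1.5) and lower power.
- **2+1 with about 157 patients.** This keeps 90% and three years, but needs about 78.5 patients a year (157/2).
- **Two years of accrual plus about 18 months of follow-up.** With 135 patients this gives about 90.4%, reads out at 3.5 years, and needs 67.5 patients a year.

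The choice depends on achievable accrual and is the sponsor's. The first is the cheapest and matches the calculation that reproduces the plan's own sample size.
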